5.9.2 Timing of blood sampling

Blood will be sampled every 5-15 minutes, dependent on the value of the previous sample according to the following ranges:

- BG \geq 325 mg/dL: every 5 minutes (+/- 2 minutes)
- BG >75 mg/dL and < 325 mg/dL: every 15 minutes (+/- 2 minutes)
- BG \leq 75 mg/dL: every 5 minutes (+/- 2 minutes)

Additional samples may be drawn for YSI glucose analysis as needed for patient safety or to recheck a suspected erroneous value (e.g. dilute sample).

In the event of loss of IV access or loss of functional YSI and need for continued subject monitoring, glucose measurements will be made on capillary whole blood using the Subject SMBG meter as needed. These values will not be included in the study data set, but will only be used for subject treatment decisions.

Samples missed due to loss of IV access or loss of functional YSI will not be considered protocol deviations.

5.9.3 Sample volume

Approximately 1.0 ml IV blood samples will be collected (after saline is cleared from sampling apparatus) in sample containers with an appropriate anticoagulant additive (BD Microtainer K2E tubes (REF 365955) or Sarstedt Monovette with K2E (REF 06.1664.001) or similar) for analysis.

5.9.4 Centrifuge

Centrifuge sample to sufficiently separate the plasma, approximately 30 seconds in StatSpin Express 2 (or similar) centrifuge (8500 rpm).

Samples centrifugation should begin as soon as possible after the blood draw (within a maximum of 3 minutes). Spun samples should be prepared, as defined in the Study Operations Manual.

*More detailed guidelines are included in the Study Operations Manual.

5.10 Sensor Replacement

For subjects with one sensor (participating in the subset), if sensor failure is suspected, sensor will not be replaced.

For subjects with two sensors, suspect failure of the primary sensor (the sensor for which calibration fingersticks are entered), the secondary sensor in the contralateral arm will become the primary sensor. Subjects will be instructed to replace the Gen 2 transmitter with

the Gen 1 transmitter in the contralateral arm. The suspect failed primary sensor will not be replaced and will be removed at the end of the study. Subjects will proceed with the next regularly scheduled visit. For the suspect failure of the secondary sensor, the sensor will be removed at the end of the study and not replaced.

5.11 Sponsor Presence at Visits

One or more technical representatives of the sponsor may be present during clinic visits under supervision of the Clinical Investigator.

5.12 Glucose challenges

The intention of the hypoglycemia and hyperglycemia challenge is to safely manipulate the subject's blood glucose levels so that sensor performance can be evaluated over a wider range than might otherwise be observed. The intentions are to induce the following:

Hypoglycemia challenge

Range	Duration (approximate)	Estimated number of paired points per subject per challenge
<60 mg/dL	30 minutes	7
<75 mg/dL	120 minutes (including 30 minutes <60 mg/dL)	25

Hyperglycemia challenge

Range	Duration (approximate)	Estimated number of paired points per subject per challenge
>325mg/dL	60 minutes	13
>180 mg/dL	120 minutes (including 60 minutes >325 mg/dL)	17

It is the intent of this protocol to induce a hyperglycemic protocol upon admission to the clinic for visits 3, 4 & 5. Subjects participating in hyperglycemia challenge soon after admission should not take subcutaneous bolus insulin approximately 3-4 hours prior to the challenge. Subjects should take their normal dose and timing of basal insulin. If challenge subjects need to eat or take insulin for safety reasons, they should inform study staff of this information on arrival to the clinic.

5.12.1 Subject eligibility

Subjects with gastroparesis will not be eligible to participate in glucose challenges. Subjects not on insulin therapy will not be expected to undergo hypoglycemic challenges. Eligible subjects will be required to participate in glucose challenges.

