4.4.12 Hyperglycemia Challenge

For qualifying subjects, a hyperglycemia challenge will be conducted to achieve a glucose goal of >350 mg/dL. Sampling interval will be q 5 min when glucose ≥ 325 mg/dL for a target of 1 hour before rescue. For those subjects not following a basal/bolus routine on MDI or CSII, glucose control will be free range. Details regarding conduct of the hyperglycemia challenge can be found in Section 5.12.

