4.5.14 Glucose Challenges

Qualifying subjects will participate in hyperglycemia and hypoglycemia challenges during the times indicated in the visit timeline table. The intention of the hypoglycemia and hyperglycemia challenge is to safely manipulate the subject's blood glucose levels so that sensor performance can be evaluated over a wider range than might otherwise be observed. Details regarding the glucose challenges can be found in Section 5.12.

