5.12.3.1 Hyperglycemia Challenge Guidelines

Glucose level	Insulin administration	Glucose administration (challenge initiation)	Duration* (Approx.)	Safety
<180 mg/dL	None. Glucose sampling period may be delayed until blood glucose is brought into range (>180 mg/dL).	Administer carbohydrates to gradually bring blood glucose into range (>180 mg/dL).		
180 mg/dL to 325 mg/dL	None	Administer meal of known carbohydrate content (and SQ insulin if appropriate, see mixed meal examples in the table in 5.11), targeting glucose level of 350 mg/dL based on subject's insulin/carbohydrate ratio. Do not withhold insulin >2-3 hours.	2 hours (including approx, 60 minutes 325-400 mg/dL)	Check/treat for ketones if subject BG >300mg/dL. Treat ketones according to the Hyperglycemia and Ketone Treatment Section 7.1.5

Glucose level	Insulin administration	Glucose administration (challenge initiation)	Duration* (Approx.)	Safety
>325mg/dL to 400 mg/dL	After approximately 60minutes in this range and achieving the targeted number of points, administer SQ fast-acting insulin targeting 120 mg/dL based on subject's insulin sensitivity ratio. Insulin may not be delivered or repeated unless approximately 3 hours after previous dose.	None	60 minutes	Check/treat for ketones if subject BG >300 mg/dL. Treat ketones according to the Hyperglycemia and Ketone Treatment Section 7.1.5
>400 mg/dL	Administer SQ fast-acting insulin targeting 120 mg/dL based on subject's insulin sensitivity ratio. Insulin may not be delivered or repeated unless 3 hours after previous dose.	None		Check/treat for ketones if subject BG >300 mg/dL. Treat ketones according to the Hyperglycemia and Ketone Treatment Section 7.1.5

*Once Hyperglycemia challenge durations have been met (120 minutes >180 mg/dL including 60 minutes >325 mg/dL), the challenge should be ended by administering SQ fast-acting insulin targeting 120-150 mg/dL based on subject's insulin sensitivity ratio. Once the subjects' BG is normal, glucose control will be free range. If additional carbohydrates are required to reach challenge goals, they may be administered.

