5.12.3.2 Hypoglycemia challenge guidelines

Glucose level	Insulin administration (challenge initiation)	Glucose administration	Duration* (Approx.)	Safety
<60 mg/dL	None	After 30 minutes and targeted points achieved, treat	30 minutes	If subject is unable to ingest glucose orally, IV

Glucose level	Insulin administration (challenge initiation)	Glucose administration	Duration* (Approx.)	Safety
		hypoglycemia using glucose tablets (15 g. and check in 15 minutes, repeat) until BG >60 mg/dL		dextrose may be used. Glucagon will be available for emergency.
60 – 75 mg/dL	None	None	120 minutes (including 30 minutes below 60 mg/dL)	
> 75 but <180 mg/dL	SQ fast-acting insulin to be delivered targeting 60 mg/dL based on subject's insulin sensitivity ratio. Bolus insulin may not be delivered or repeated unless 3 hours after previous dose.	None		

*Once Hypoglycemia challenge durations have been met (120 minutes <75 mg/dL including 30 minutes <60 mg/dL), the challenge should be ended by inducing a controlled raising of the subject's BG to the normal range (75-120 mg/dL) using glucose tablets or food. Once the subjects BG is normal, glucose control will be free range.

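### Protocol 5.12.1 and the visit sections disagree on whether subjects not on a basal/bolus regimen undergo glucose challenges, and the challenge tables give no stated dosing basis for subjects without insulin ratios

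*Protocol*

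**What the plan says.** Entry (Protocol 3.2.1) asks for adulthood, diabetes for at least one year and consent. Insulin therapy is not required, and 5.12.1 itself provides for subjects who take none.

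Section 5.12.1, the section on challenge eligibility, sets two limits and one duty. The first limit bars anyone with gastroparesis from every challenge. The second limit and the duty read: "Subjects not on insulin therapy will not be expected to undergo hypoglycemic challenges. Eligible subjects will be required to participate in glucose challenges".

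The visit sections use a different test. For Visit 3, section 4.4.12 (hyperglycemia) says: "For those subjects not following a basal/bolus routine on MDI or CSII, glucose control will be free range". The same sentence stands in 4.4.13 (hypoglycemia, Visit 3) and in the 4.6 timeline for the challenge window of Visits 6-8.

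For Visits 4-5 there is no such sentence. Section 4.5.14 says "Qualifying subjects will participate in hyperglycemia and hypoglycemia challenges during the times indicated in the visit timeline table" and sends the reader to 5.12 for details.

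On dosing, 5.12.3.1 sizes the challenge meal on the subject's insulin/carbohydrate ratio and says of completion that "the challenge should be ended by administering SQ fast-acting insulin targeting 120-150 mg/dL", based on the subject's insulin sensitivity ratio. Section 5.12.3.2 starts the hypoglycemia challenge with "SQ fast-acting insulin to be delivered targeting 60 mg/dL based on" the same ratio. Screening (4.1) records correction factors and carbohydrate ratios only where they apply.

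**The concern.** Two groups fall between the rules: subjects on no insulin, and subjects on basal insulin only. Under 5.12.1 they appear to owe one or both challenges; under the Visit 3 and Visits 6-8 text they do none. Up to four sites will read these passages, and two sites could treat similar subjects differently, or one site could treat the same subject differently from visit to visit.

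What is at stake is first who is exposed to deliberately induced glucose above 325 or below 60 mg/dL, and whether the written challenge procedure can be followed for that person. Second, challenges are meant to widen the glucose range in which the sensor is tested. If eligibility changes by visit, the glucose mix behind the by-visit accuracy table (Table 8) changes with it.

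**Working it through.** **Passages side by side** (subjects without gastroparesis)

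| Therapy | 5.12.1 | 4.4.12, 4.4.13 (Visit 3) and 4.6 timeline (Visits 6-8) | 4.5 (Visits 4-5) |
|---|---|---|---|
| No insulin | Hyperglycemia required by implication; hypoglycemia exempt | Free range | No therapy rule; refers to 5.12, hence hyperglycemia |
| Basal only | Both required by implication | Free range | No therapy rule; refers to 5.12, hence both |
| Basal/bolus (MDI or CSII) | Both | Both at Visit 3; one or the other at Visits 6-8 | Both |

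The last row is consistent; the first two are not. Read across, the same subject can be free range at Visit 3, eligible at Visits 4-5, and free range at Visits 6-8.

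Section 5.12.3 adds a further conflict. At Visits 6-8 it selects the challenge from the first glucose value alone: below 180 mg/dL hypoglycemia, otherwise hyperglycemia. A non-insulin subject who arrives below 180 mg/dL is thus assigned the hypoglycemia challenge by 5.12.3, exempted from it by 5.12.1, and put into free range by 4.6.

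**Size in paired points**

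The per-challenge figures in 5.12 reproduce as duration ÷ sampling interval + 1:
- Above 325 mg/dL: 60/5 + 1 = 13.
- Above 180 mg/dL: 13 + 60/15 = 17.
- Below 60 mg/dL: 30/5 + 1 = 7.
- Below 75 mg/dL: 120/5 + 1 = 25.

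These count one series of reference samples, so one sensor. Over Visits 3-5 the two readings differ, per affected sensor, by up to:
- 3 × 13 = 39 pairs above 325 mg/dL, for either group.
- 3 × 25 = 75 pairs below 75 mg/dL, of which 3 × 7 = 21 are below 60 mg/dL, for basal-only subjects only. Non-insulin subjects are outside the hypoglycemia challenge under both 5.12.1 and the free-range sentences.

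These are ceilings. Section 11.1.4 expects 127 + 65 = 192 pairs at 301-400 mg/dL in each Visit 3-5 session, over 66 sensors. Three sessions give 3 × 192 = 576, and 576/66 ≈ 8.7 per sensor. Full yield on every sensor would be 66 × 13 = 858 per session, so the plan does not expect 13 from each. The comparison is rough: 8.7 averages challenged and unchallenged sensors, and 301-400 is a different band from above 325.

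The documents do not give the number of affected subjects. As an assumption only, take 0 to 11 of 36 (0 to about 30%) and count pairs over Visits 3-5:

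| Yield per sensor | One sensor each | Two sensors each |
|---|---|---|
| Intended, 39 | 0 to 11 × 39 = 429 | 0 to 858 |
| Plan average, 8.7 (576/66) | 0 to 11 × 576/66 = 96 | 0 to 192 |

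**The case against.** The strongest reply is that the texts can be applied together. Section 5.12.1 binds only eligible subjects, the visit sections speak of *qualifying* subjects, and 4.4.14, 4.5.15 and 4.6.14 send subjects unable to take part to free range. On that view gastroparesis is one filter and basal/bolus another, and 4.5 merely omits a sentence. Part of this stands: 5.12.1 names neither hyperglycemia for non-insulin subjects nor basal-only subjects, so the duty arises by implication, and 4.5 permits the Visit 4-5 challenge by silence rather than directing it. It does not remove the conflict. Neither *qualifying* nor *unable* is defined by therapy type, and if basal/bolus were the universal gate, the hypoglycemia exemption for non-insulin subjects would be redundant.

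A reader might infer that a non-insulin subject would be driven high with an ending dose that cannot be calculated. The documents do not support that. Section 7.1 leaves ultimate responsibility with the investigator, and 7.1.5 lets the investigator treat when clinically indicated. Section 7.1.5.1 discontinues the challenge at 400 mg/dL or after more than two hours above 300 mg/dL, and 7.2.1 lets the subject end it. Nor does every insulin step rest on the subject's own ratio: for ketones of 1.5 mmol/L or more, 7.1.5.1 allows a clinician-determined factor. What stands is that the challenge tables state no basis for subjects without the ratios. Discretion mitigates this but does not settle who enters a challenge.

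A reader might also infer that visit-level MARD is distorted. The glucose mix already differs by design, with both challenges at Visits 3-5 and one at Visits 6-8. Results are stratified by YSI range (Protocol 11.3.2.4, SAP 6.10.1.3), and SAP Table 2.8 crosses agreement with YSI range by day through Day 30. MARD is descriptive, with no hypothesis. The supportable statement is that the mix may shift further.

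Finally, the pair counts above should not be set against all 623 + 319 = 942 planned pairs at 301-400 mg/dL. That total covers six visits; the figure for Visits 3-5 is 576.

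**Conclusion.** Challenge eligibility is internally contradictory for subjects on no insulin and on basal insulin only, and it varies by visit as written. Section 5.12.3 adds a separate conflict for non-insulin subjects below 180 mg/dL. The contradiction stands whatever the number affected, but its practical size depends on that number, which is not given and may be zero. Per affected sensor over Visits 3-5 the high-glucose difference is at most 39 pairs, assuming full intended yield at all three visits. The plan's own average of about 8.7 suggests the realised difference may be much smaller, though challenged subjects may exceed the average. Low-glucose pairs are at issue for basal-only subjects only. No power or error rate is involved. The reason to act is that the instructions conflict on who is exposed to an induced glucose extreme.

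**What to change.** These passages must be reconciled. The sponsor should decide on one challenge-eligibility rule by therapy type (no insulin, basal only, basal/bolus) and state it once in 5.12.1. Sections 4.4.12, 4.4.13, 4.5.14, the 4.6 timeline and 5.12.3 should then refer to it rather than carry rules of their own. Sections 5.12.3.1, 5.12.3.2 and 7.1.5.1 should be made consistent with it, so that the basis for meals and insulin is stated for every therapy type that can enter a challenge. Which rule is right is a clinical decision that this review does not make.

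The cost is protocol wording, approved as an amendment under 13.4, with no added procedures. If the narrower rule is kept, there may be fewer extreme-glucose pairs.

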5.12.2 Challenge periods (Visits 3, 4 & 5)

Subject blood glucose level as measured by the first blood glucose sample reading will determine whether or not the subject will begin the hyperglycemia challenge. If blood glucose is <180 mg/dL the glucose sampling period may be delayed until blood glucose is brought into range.

5.12.3 Determining which challenge to choose (Visits 6, 7 & 8)

Subject BG level as measured by the first blood glucose sample reading will determine whether or not the subject will participate in the hypoglycemia or hyperglycemia challenge on that study day, according to the following table:

Glucose level	Challenge
<180 mg/dL	Hypoglycemia challenge
≥180 mg/dL	Hyperglycemia challenge

5.12.3.1 Hyperglycemia Challenge Guidelines

Glucose level	Insulin administration	Glucose administration (challenge initiation)	Duration* (Approx.)	Safety
<180 mg/dL	None. Glucose sampling period may be delayed until blood glucose is brought into range (>180 mg/dL).	Administer carbohydrates to gradually bring blood glucose into range (>180 mg/dL).		
180 mg/dL to 325 mg/dL	None	Administer meal of known carbohydrate content (and SQ insulin if appropriate, see mixed meal examples in the table in 5.11), targeting glucose level of 350 mg/dL based on subject's insulin/carbohydrate ratio. Do not withhold insulin >2-3 hours.	2 hours (including approx, 60 minutes 325-400 mg/dL)	Check/treat for ketones if subject BG >300mg/dL. Treat ketones according to the Hyperglycemia and Ketone Treatment Section 7.1.5

Glucose level	Insulin administration	Glucose administration (challenge initiation)	Duration* (Approx.)	Safety
>325mg/dL to 400 mg/dL	After approximately 60minutes in this range and achieving the targeted number of points, administer SQ fast-acting insulin targeting 120 mg/dL based on subject's insulin sensitivity ratio. Insulin may not be delivered or repeated unless approximately 3 hours after previous dose.	None	60 minutes	Check/treat for ketones if subject BG >300 mg/dL. Treat ketones according to the Hyperglycemia and Ketone Treatment Section 7.1.5
>400 mg/dL	Administer SQ fast-acting insulin targeting 120 mg/dL based on subject's insulin sensitivity ratio. Insulin may not be delivered or repeated unless 3 hours after previous dose.	None		Check/treat for ketones if subject BG >300 mg/dL. Treat ketones according to the Hyperglycemia and Ketone Treatment Section 7.1.5

*Once Hyperglycemia challenge durations have been met (120 minutes >180 mg/dL including 60 minutes >325 mg/dL), the challenge should be ended by administering SQ fast-acting insulin targeting 120-150 mg/dL based on subject's insulin sensitivity ratio. Once the subjects' BG is normal, glucose control will be free range. If additional carbohydrates are required to reach challenge goals, they may be administered.

5.12.3.2 Hypoglycemia challenge guidelines

Glucose level	Insulin administration (challenge initiation)	Glucose administration	Duration* (Approx.)	Safety
<60 mg/dL	None	After 30 minutes and targeted points achieved, treat	30 minutes	If subject is unable to ingest glucose orally, IV

Glucose level	Insulin administration (challenge initiation)	Glucose administration	Duration* (Approx.)	Safety
		hypoglycemia using glucose tablets (15 g. and check in 15 minutes, repeat) until BG >60 mg/dL		dextrose may be used. Glucagon will be available for emergency.
60 – 75 mg/dL	None	None	120 minutes (including 30 minutes below 60 mg/dL)	
> 75 but <180 mg/dL	SQ fast-acting insulin to be delivered targeting 60 mg/dL based on subject's insulin sensitivity ratio. Bolus insulin may not be delivered or repeated unless 3 hours after previous dose.	None		

*Once Hypoglycemia challenge durations have been met (120 minutes <75 mg/dL including 30 minutes <60 mg/dL), the challenge should be ended by inducing a controlled raising of the subject's BG to the normal range (75-120 mg/dL) using glucose tablets or food. Once the subjects BG is normal, glucose control will be free range.

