7.1.4.1 Guidelines for treatment for hypoglycemia

During hypoglycemia challenge or monitoring period, site will follow section 5.12 hypoglycemia challenge table. Subject safety prevails and Investigator may treat for hypoglycemia when clinically indicated.

Subjects will be treated for hypoglycemia as appropriate according to the following table:

Glucose level	Glucose administration	Safety
<60 mg/dL	Treat hypoglycemia as appropriate using oral carbohydrates such as glucose tablets or juice (~15 g. and check glucose in 15 minutes minimum, repeat) until BG >60 mg/dL	If subject is unable to ingest glucose orally, IV dextrose (~2-3 mL/kg D10 intravenous or up to 30 ml D50%) may be used. Glucagon will be available for emergency.
60 – 75 mg/dL	Treat hypoglycemia as appropriate using oral carbohydrates such as glucose tablets or juice (~10 g. and check glucose in 15 minutes minimum, repeat) until BG >60 mg/dL	

- Glucose <60 mg/dL will be treated orally with fast acting carbohydrate as tolerated by the subject and as needed until a glucose level of ≥ 75 mg/dL is achieved.
- Risk for severe hypoglycemia is defined as any of the following situations:
 - Glucose <50 mg/dL
 - The subject is unable to cooperate with oral treatment of hypoglycemia
 - The glucose is dropping at a rate that may not respond adequately to oral treatment
 - The subject experiences symptoms of neuroglycopenia (e.g. lethargy, disorientation, confusion [disordered processing of information or communication], or inappropriate behavior)
 - The subject experiences symptoms of severe hypoglycemia (i.e. hypoglycemic seizure or loss of consciousness)

- In the event that there is NO intravenous access and the subject is at risk for severe hypoglycemia (as defined above), the subject will be treated with 1 mg of glucagon subcutaneously or intramuscularly.
 - The drug will be reconstituted and administered per package insert/instructions.
 - Glucagon may be repeated as needed every 20 minutes to achieve glucose level ≥ 75 mg/dL. Once the subject is able to consume oral treatment, the subject will be treated orally with fast acting carbohydrate as needed until a glucose level of ≥ 75 mg/dL is achieved. Orange juice and milk will be avoided after glucagon administration.
 - Attempts will be made to reestablish intravenous access.

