7.2 Subject Stopping Rules

7.2.1 Stopping challenges

Glucose challenges will be stopped and subject will enter free range glucose control if:

- Subject meets the challenge completion criteria:
 - Hypoglycemia challenge - approximately 120 minutes < 75 mg/dL including 30 minutes < 60 mg/dL
 - Hyperglycemia challenge – approximately 120 minutes > 180 mg/dL including 60 minutes > 325 mg/dL
- Subject requests to end the challenge due to discomfort (desires food and/or insulin)
- Subject ketone measurement ≥ 0.6 mmol/L and glucose is > 300 mg/dL

These subjects will be eligible to continue participating in challenges at future accuracy (sampling) visits. Blood sample collecting and analysis on YSI will continue during this time.

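### With IV access in place, the hypoglycemia challenge withholds glucose below 60 mg/dL for about 30 minutes with no floor, and a value below 50 mg/dL triggers no stop

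*Protocol*

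**What the plan says.** Protocol 5.12.3.2 sets the challenge rules by glucose band. Above 75 and below 180 mg/dL the instruction is "SQ fast-acting insulin to be delivered targeting 60 mg/dL based on" the subject's insulin sensitivity ratio. Below 60 mg/dL no insulin is given, and oral glucose is timed as "After 30 minutes and targeted points achieved, treat". The Safety column of that row allows IV dextrose if the subject cannot swallow, and keeps glucagon for emergencies. Neither depends on a glucose value.

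The visit timelines in 4.4, 4.5 and 4.6 repeat the hold as a target of 24 YSI values below 75 mg/dL, six of them below 60 mg/dL, before rescue.

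Section 7.1.4.1 says which rule governs: "During hypoglycemia challenge or monitoring period, site will follow section 5.12 hypoglycemia challenge table". The next sentence is the override: "Subject safety prevails and Investigator may treat for hypoglycemia when clinically indicated". The section then states: "Risk for severe hypoglycemia is defined as any of the following situations". Glucose below 50 mg/dL heads that list of five. The mandated action tied to the list begins "In the event that there is NO intravenous access and the subject is at risk for severe hypoglycemia" and is glucagon. A separate bullet says "Glucose <60 mg/dL will be treated orally with fast acting carbohydrate as tolerated by the subject and as needed", without saying when.

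Sections 7.2.1 to 7.2.4 list what ends a challenge, a visit or participation. None names a low glucose value.

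**The concern.** The challenge induces hypoglycemia for data collection, and section 8.1 says subjects gain no direct benefit. Eligible subjects must take part (5.12.1). Hypoglycemia challenges are scheduled at Visits 3 to 5 and, when the first glucose is below 180 mg/dL, at Visits 6 to 8, so up to six per subject.

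The protocol defines a glucose value that signals risk for severe hypoglycemia, but attaches no stop to it while IV access works. Consider a cooperative subject whose glucose drifts slowly below 50 mg/dL without neuroglycopenia. The written default is to keep waiting for the clock and the sample count. Treating that subject sooner depends on someone choosing to depart from the default.

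**Working it through.** **Reproducing the planned counts.** Section 5.12 expects 7 points in 30 minutes below 60 mg/dL and 25 in 120 minutes below 75 mg/dL. At one sample every 5 minutes, counting both ends: 30/5 + 1 = 7 and 120/5 + 1 = 25. Without the extra end point the counts are 6 and 24, the targets in the visit timelines. Both sets are consistent with a planned 30-minute hold.

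**Length of the default hold.** It is the longer of about 30 minutes and the time to collect the points below 60 mg/dL. Section 5.9.2 allows 5 minutes ± 2 between samples.
- Six values, five intervals: 5 × 5 = 25 minutes nominal, 5 × 7 = 35 at the late limit.
- Seven points, six intervals: 6 × 5 = 30 minutes nominal, 6 × 7 = 42 at the late limit.

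The hold is therefore about 30 minutes, and about 35 to 42 if every sample is late. This assumes no missed sample and takes the targeted points to be those below 60 mg/dL. Section 4.4.13 speaks of two hours at or below 75 mg/dL before rescue; the narrower reading used here gives the shorter hold.

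**The five risk situations in 7.1.4.1 against the stops in 7.2.**
- Glucose below 50 mg/dL: no stop in 7.2.1, 7.2.2, 7.2.3 or 7.2.4.
- Unable to cooperate with oral treatment: 7.2.2.
- Fall too fast for oral treatment: 7.2.2.
- Neuroglycopenia: 7.2.2.
- Seizure or loss of consciousness: 7.2.3 and 7.2.4.

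**The hyperglycemia side.** The hold row in 5.12.3.1 ends at 400 mg/dL. The row above 400 mg/dL calls for insulin with no wait for data, subject only to the 3-hour limit on repeat insulin. Section 7.1.5.1 ends the challenge at 400 mg/dL or more at any time.

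**Planned exposure.** Section 11.1.4 expects, at 40-60 mg/dL and for 66 sensors, 166/66 = 2.5 pairs per sensor in each 16-hour session and 106/66 = 1.6 in each 12.5-hour session. These averages include subjects who are not challenged and leave out values below 40 mg/dL. They do not show how many challenges cross 50 mg/dL.

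**Data cost of a stop below 50 mg/dL.** The crossing value is itself one of the 24 targeted values below 75 mg/dL, so at most 24 − 1 = 23 YSI values are forgone, or 23 × 2 = 46 pairs with two sensors. (Against the 25 points in 5.12 the figure is 24.) A loose study-wide ceiling is every planned pair in the two lowest bins: 815 + 2,194 = 3,009, and 3,009/22,786 = 13.2%. The real loss arises only in crossing challenges.

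**The case against.** The strongest reply is that safety already overrides the table. The sentence after the instruction to follow 5.12 puts subject safety first and lets the investigator treat. A physician or nurse practitioner is to be present during challenges, and each site is to have a detailed safety plan (8.3; see also 7.1.1). Sampling is every 5 minutes. Insulin is dosed to a 60 mg/dL target, none is given for the challenge at 75 mg/dL or below, and boluses are at least 3 hours apart. Recent severe hypoglycemia is an exclusion, as are conditions judged to raise the risk of induced hypoglycemia. Rapid fall and neuroglycopenia stop the challenge, and the subject can ask to stop. The omission may also be deliberate, since accuracy is evaluated from 40 mg/dL upward.

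Much of this stands, and it makes the exposed case narrow. A reader might infer that the protocol forbids treatment below 50 mg/dL. It does not; the override permits it. A reader might also infer that the row above 400 mg/dL lets insulin be given without any wait. It does not, because the 3-hour limit applies. The contrast is only that no data-collection hold operates there and that a numeric stop exists.

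What remains is that none of these controls sets a floor in these documents. The 60 mg/dL insulin target is a dosing aim, and completion requires about 30 minutes below it. The bullet on oral treatment below 60 mg/dL has no timing: if it overrides the table it contradicts the hold, and if it does not the gap stays. No challenge target is set below 50 mg/dL, so the planned targets do not require the hold to continue there.

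One further objection is right and shapes the remedy. Section 5.9.2 anticipates erroneous values such as dilute samples, so a single reading should not by itself end the challenge.

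**Conclusion.** The concern holds in a limited form. During a challenge with working IV access, the default is to withhold glucose below 60 mg/dL for about 30 minutes (about 35 to 42 at the late sampling limit) with no lower bound. Glucose below 50 mg/dL is the only one of the protocol's five severe-risk situations without a stop in 7.2. It matters for a cooperative, slowly falling subject without neuroglycopenia, who is protected by discretion, clinician presence, site plans and the subject's own request.

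Two stronger conclusions are not supported. The documents give no basis for a rate of crossings or of harm. Nor do they already treat 50 mg/dL as a stopping value: 7.1.4.1 uses it to define risk and to trigger glucagon without IV access. Using it to end the hold is a proposal built on the protocol's own number. Site safety guidelines may contain a floor, but they are not part of these documents. This is a worthwhile, low-cost safety correction.

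**What to change.** 1. In 5.12.3.2, split the row below 60 mg/dL. From 50 to below 60 mg/dL, keep the present hold. Below 50 mg/dL, treat at once by the routes already listed, without waiting for 30 minutes or for the targeted points: oral glucose 15 g with a 15-minute check, IV dextrose if the subject cannot ingest, and glucagon under 7.1.4.1 if IV access is lost.
2. On the first value below 50 mg/dL, draw an immediate recheck YSI sample under 5.9.2, without delaying treatment.
3. In 7.2.1, add that a confirmed glucose below 50 mg/dL ends that day's hypoglycemia challenge, with reattempt allowed at later visits.
4. In 4.4, 4.5 and 4.6, align the wording on targets before rescue with the new row.
5. In 4.4 and 4.5, state that YSI sampling continues through recovery after such a stop, as 7.2.1 provides. Those timelines otherwise end YSI collection when the challenge concludes.

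Detection would then take about one sampling interval, 5 minutes (3 to 7 with the window), and treatment would follow the result.

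The drafting cost is one table row, one list item, three timeline cells and two added sentences. The data cost falls only on challenges that cross 50 mg/dL: fewer pairs at 40-49 mg/dL and some lost at 50-75 mg/dL, within the per-challenge limit worked out above. The 40-60 mg/dL bin would shift toward its upper half, which the report should state. Sampling every 5 minutes during recovery, while glucose is 75 mg/dL or below, offsets part of the loss.
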